1.0 INTRODUCTION

Prior to surgery or other invasive procedures, skin must be treated with topical antimicrobial products (Pre-Operative Skin Preparations) to prevent nosocomial infections by reducing the number of microorganisms on the skin. The proposed Tentative Final Monograph (TFM) for *Health-Care Antiseptic Drug Products* (Vol. 59, No. 116, June 17, 1994) describes an *in vivo* procedure for evaluating this type of product as well as expected performance criteria. When a new product is tested a predicate preoperative skin preparation must be included in the study as a positive control.

[figure not shown]
2.0 OBJECTIVE

The purpose of this study is to compare the antimicrobial effectiveness potential of three investigational test products identified as "ChloraPrep Triple Swabsticks" using two application procedures (three swabsticks at once and the three swabsticks used sequentially). "Hibiclens" will be evaluated to serve as the reference product (positive control). "Sterile Triple Swabsticks Saturated with 5.25 mL of Sterile Deionized Water" ("Sterile Swabsticks with Sterile Deionized Water") using two application procedures (three swabsticks at once and the three swabsticks used sequentially) will be evaluated to serve as a negative control. This evaluation will be conducted based on methodology specified by the Food and Drug Administration Office of Drug Evaluation and Research.

4.1 NAME OF THE IRB: MICROBIOTEST INTERNAL IRB

5.0 CLINICAL RESEARCH STANDARDS

The clinical investigation, including the informed consent, will be reviewed by the Institutional Review Board in accordance with Title 21 of the Code of Federal Regulations, Parts 50 and 56. Written approval by the Board must be obtained prior to the initiation of the study. The study will be conducted in accordance with the Good Clinical Practice Regulations, the Standard Operating Procedures of MICROBIOTEST, the study protocol and any protocol amendments.

6.0 SCOPE

This evaluation will measure the antimicrobial effectiveness of a preoperative skin product as specified by the Food and Drug Administration Tentative Final Monograph (TFM) for *Effectiveness Testing of a Patient Preoperative Skin Preparation* (FR 59:116, 17 June 94, pp. 31450-31452).

This study will evaluate the antimicrobial effectiveness of the three test and control articles: "ChloraPrep Triple Swabsticks" using two application procedures (three swabsticks at once and the three swabsticks used sequentially), "Hibiclens", and "Sterile Swabsticks with Sterile Deionized Water" using two application procedures (three swabsticks at once and the three swabsticks used sequentially). A minimum of 278 human subjects will be employed utilizing bilateral product applications assuring that the each test and control articles will be evaluated on sites as described in the following table.

Test Articles (Application)	Number of Evaluations on Abdomen	Number of Evaluations on Groin
ChloraPrep Triple Swabsticks (three swabsticks applied all at once)	111	111
ChloraPrep Triple Swabsticks (three swabsticks applied sequentially)	111	111
Hibiclens (applied according to package directions)	111	111
Sterile Swabsticks with Sterile Deionized Water (three swabsticks applied all at once)	111	111
Sterile Swabsticks with Sterile Deionized Water (three swabsticks applied sequentially)	111	111

Each of the test articles will be evaluated at the groin and the abdominal sites for immediate antimicrobial effect by sampling at ten minutes \pm thirty seconds and six hours \pm thirty minutes after completion of application. All product applications will be performed using randomized placement.

7.0 TEST ARTICLES

7.1 Test Product:

7.1.1 ChloraPrep Triple Swabsticks (2% Chlorhexidine gluconate (CHG) and 70% isopropyl alcohol).

7.2 Reference Product (Positive control):

7.2.1 Hibiclens (4% CHG).

7.3 Negative control:

7.3.1 Sterile Swabsticks with Sterile Deionized Water.

8.0 LABORATORY SUPPLIES AND EQUIPMENT (PROVIDED BY MICROBIOTEST)

8.1 Equipment

- 8.1.1 Colony counter.
- 8.1.2 Incubator - capable of maintaining a temperature of $30 \pm 2^\circ\text{C}$ may be used.
- 8.1.3 Sterilizer - gravity steam sterilizer capable of producing the conditions of sterilization.
- 8.1.4 Stop-clock - One that can be read for hours and minutes.
- 8.1.5 Water bath - A bath of appropriate size and capable of maintaining temperature $\pm 2^\circ\text{C}$.
- 8.1.6 Bacteriological pipettes - Sterile pipettes of suitable size.
- 8.1.7 Dilution bottles - A container that can be sterilized, having a 150 to 200 mL capacity and a tight closure may be used.
- 8.1.8 Test tubes and closures - Sterile and of suitable size.
- 8.1.9 Vortex mixer
- 8.1.10 Sterile hollow stainless steel cylinders 2.2 cm in diameter and approximately 2.54 cm in height.
- 8.1.11 Sterile rubber policeman.
- 8.1.12 Sterile polystyrene Petri dishes, approximately 100 mm x 15 mm.
- 8.1.13 Occlusive sterile catheter dressing - Opsite, or suitable alternative.

8.2 Reagents and Media

- 8.2.1 Kit products for Washout Period: non-antimicrobial bar soap, shampoo, and deodorant.
- 8.2.2 Scrub solution - [REDACTED]

- 8.2.2.1 Dilution fluid - Butterfield's Phosphate Buffered water containing 1.25 mL AOAC Phosphate Buffer Stock in one liter purified water containing appropriate neutralizers: 10mL of Polysorbate, 3 G of lecithin and 10 G of Tamol. The dilution fluid will have a final pH of 7.2 ± 0.1 .
- 8.2.3 Plating medium - Soybean-Casein Digest Agar (or equivalent) containing 0.5% Polysorbate 80 and 0.07% lecithin to stimulate growth of lipophilic organisms.
- 8.2.4 Plating medium - Soybean-Casein Digest Agar (or equivalent)

9.0 NEUTRALIZATION

The objective of this evaluation is to determine the ability of the sampling solutions to completely neutralize the active ingredients contained in the test products and positive control when applied to the abdomen of test subjects without exhibiting toxicity to the marker organism. The test microorganism used for the neutralization study will be *Staphylococcus epidermidis*, ATCC 12228, a common skin bacterium. The procedure to be used is shown in Appendix 2.

10.0 SUBJECT SELECTION

10.1 Number of Subjects

The requirement of 111 subjects per test article configuration (test arm) to finish this study was determined by the sample size equation at the recommendation of both the FDA Proposed Rule and ASTM E1173; the following formula was used for group size calculations:

$$n \geq s^2 \frac{(Z_{\alpha/2} + Z_{\beta})^2}{\Delta^2}$$

Where:

- n = minimum number of required samples in each test arm (rounded up).
- s = standard deviation of the acquired data (0.735).
- $Z_{\alpha/2}$ = the Z statistic for a two-sided 95% confidence interval (1.96), where α (0.05) is the probability of allowing a Type I error (predicting significance when there is none).
- Z_{β} = the Z statistic for the power of the test (0.842), where β (0.80) is the power, i.e., the probability of allowing a Type II error (failing to predict significance when it exists).
- Δ = the difference being tested for (0.196).

The best reasonable estimate of the number of subjects needed per test article configuration (study arm), based on available current data is 111.

Since there are five study arms, the minimum number of subjects based on bilateral applications is 278 (Five arms x 111 / 2).

Initial screening baseline counts will be collected from a number of healthy subjects of at least the age of sixteen sufficient to provide at least 278 qualified subjects to enter the treatment phase of the study. (NOTE: As it is anticipated that not all subjects that have qualifying screening-day baseline counts will have qualifying test-day baseline counts, it may be necessary to treat more than 278 subjects.)

The eligibility of each subject will be determined from a medical history collected on the Screening Inclusion/Exclusion Form and Treatment Inclusion/Exclusion Form (to be provided prior to study initiation).

10.2 Criteria for Inclusion

Potential subjects may be included in this study if they meet the following requirements:

- 10.2.1 Males and/or females, of at least 16 years of age. Subjects less than 18 must have written custodial consent.
- 10.2.2 Are cooperative and willing to answer questionnaires and sign a consent form (to be provided prior to study initiation).
- 10.2.3 Are in general good health.
- 10.2.4 Have skin within 6 inches of the test sites that is free of tattoos, dermatoses, abrasions, cuts, lesions or other skin disorders.

10.3 Exclusions

Individuals cannot be enrolled in the study if they:

- 10.3.1 Have been exposed to topical or systemic antimicrobials during the two-week pretest-conditioning period. This restriction includes, but is not limited to, shampoos, lotions, soaps, body powders, and materials such as solvents, acids, or alkalis.
- 10.3.2 Have been medically diagnosed as having a medical condition, which would preclude participation such as: diabetes, hepatitis, an organ transplant, a medical surgical implant or an immune-compromised system.
- 10.3.3 Have any medical condition that in the opinion of the Investigator would preclude participation.
- 10.3.4 Have bathed in chemically treated pools or hot tubs two weeks prior to any microbial sampling.
- 10.3.5 Have used UV tanning lamps two weeks prior to any microbial sampling.
- 10.3.6 Have bathed or showered less than 48 hours prior to any microbial sampling.
- 10.3.7 Have a known sensitivity to CHG.
- 10.3.8 Have a known sensitivity to latex products.
- 10.3.9 Have a known sensitivity to fragrances.
- 10.3.10 Are pregnant or nursing.
- 10.3.11 Are not willing to fulfill the requirements of the protocol.
- 10.3.12 Subjects who have completed part or all of the study will not be reentered in the study.

11.0 SUBJECT WITHDRAWAL

After admission to the study, a subject may withdraw at any time for any reason, but must report such reason fairly and accurately.

12.0 PROCEDURES

12.1 Pre-Test Period

A period of at least two weeks prior to the first baseline sampling will be designated the "pre-test" period. During this time subjects will be instructed to use only personal hygiene products supplied by the Investigator for personal hygiene (soaps, shampoos, deodorants, etc.) and will be told to avoid skin contact with solvents, acids, and bases. Subjects will be prohibited from using UV tanning lamps, and from bathing in chemically treated pools and/or hot tubs. Additionally, subjects will not be allowed to bathe or shower forty-eight hours prior to being sampled. They will be allowed to take sponge baths; however, they must not disturb the test sites.

Subjects must not shave the anatomical sites within five days prior to being treated with the test products. This regimen will allow for the stabilization of the normal microbial flora of the skin.

12.2 Baseline Week

12.2.1 The week following the pre-test period will constitute the baseline week. Subjects will not shower within forty-eight hours of being sampled. All subjects will be sampled for screening baseline at least seventy-two hours prior to treatment with the Test Articles.

12.2.2 Samples taken from the two contralateral abdominal and groin sites will be collected. Based upon adequate screening baseline count on contralateral abdominal and groin sites, a subject will be eligible to continue the study. Criteria for acceptance of screening counts will be at least 1.0×10^5 CFU/cm² on contralateral sites in the groin region and 1.0×10^3 CFU/cm² on contralateral abdominal sites. A second and final baseline sample using the same criteria as for screening baseline will be collected at each test area prior to being prepped on the day of treatment.

Post-treatment count data will be excluded from the data analysis if they are derived from any area that fails to exhibit a level of bacteria at the second baseline sampling sufficient (1.0×10^5 CFU/cm² on contralateral sites in the groin region and 1.0×10^3 CFU/cm² on contralateral abdominal sites) to permit detection of a $3.0 \log_{10}$ reduction in the groin region and a $2.0 \log_{10}$ reduction in the abdominal sites.

The table below summarizes the minimum baseline criteria for each of the test sites along with the minimum effective \log_{10} reduction criteria stipulated by the FDA.

Anatomical Site	Minimum Baseline	Minimum \log_{10} Reduction
Abdomen	1.0×10^3 CFU/cm ²	$2.0 \log_{10}$ @ 10 minutes*
Groin	1.0×10^5 CFU/cm ²	$3.0 \log_{10}$ @ 10 minutes*

*Note: 6 hour samples may not exceed the test day baseline.

12.2.3 All sample sites requiring clipping will be clipped at least forty-eight hours prior to test day.

12.2.4 All sampling will be performed using the cylinder sampling technique (Section 12.4.1).

12.3 Test Period

12.3.1 Prior to being sampled, the subjects will be questioned regarding their adherence to protocol restrictions. Subjects will be visually examined again (by a technician) at the anatomical sampling sites to ensure no evidence of injury or dermatoses is present.

12.3.2 Randomization: According to a computer-generated randomization schedule, test areas on each subject's groin and abdominal regions will be delineated to receive one of the five test articles on each side. Randomization will be balanced between left and right sides. Treatment day baseline and post prep sampling sites will be randomized within each test area.

12.3.3 Blinding: The test material cannot be blinded from the investigator because of the obvious difference in applicator design and color. The investigator treating the subject will not be involved in bacterial enumeration and counting the plates of that particular subject.

12.3.4 The dimensions of each treatment area will be 2" x 5" on the upper inner part of the thigh below the inguinal ligament. The dimension of each treatment area will be 5" x 5" on side of umbilicus on the abdomen. Four sampling sites will be delineated within each treatment area.

[figure not shown]
12.3.5 Based upon the design stipulated in the Section 6.0, the groin region and abdomen will be sampled for the final baseline (second baseline). The appropriate areas will be prepped using the test articles (Appendix 1). The sites will be sampled as stipulated in Section 6.0.

12.3.6 For the 6 hour \pm 30 minutes sites, sterile gauze pads will be placed over the prepped areas to aid prevention of microbial contamination. The gauze pads will be held in place with an occlusive sterile catheter dressing. All samples will be taken from sites using the cylinder sampling technique (Section 12.4.1).

NOTE: Timed sampling will begin when prepping is completed as defined in the instructions for prepping (See Appendix 1).

Diagrams of the treatment regions are provided below:

12.4 Microbiological Methods

12.4.1 Sample collection

Quantitative cultures will be obtained by a modification of the cylinder sampling technique of Williamson and Kligman¹. A sterile scrubbing cup (3.8 cm², internal area, height approximately 2.54 cm.) will be held firmly to the skin over the site to be sampled.

Three mL of scrub solution containing neutralizers (Section 8.2.2) will be placed into the cup, and the area scrubbed with moderate pressure for one minute using a sterile rubber "policeman." The scrub solution will be aspirated and replaced with 3.0 mL of fresh solution and the scrub repeated. The two aliquots will be pooled. These procedures will be used for all baseline samples and treatment samples. Aliquots of the pooled scrub solutions will be diluted in 10-fold steps, using Butterfield's Phosphate Buffered Dilution water (Section 8.2.2.1) containing neutralizers as the diluent.

¹ Williamson P., Kligman P.M.: A New Method for the Quantitative Investigation of Cutaneous Bacteria. *J. Invest. Dermatol.* 45:498-503, 1965.

12.4.2 Enumeration of Microorganisms

One mL aliquots of appropriate dilutions will be plated in duplicate in 15-20 mL Soybean-Casein Digest Agar pour plates containing appropriate neutralizers within 30 minutes of the sampling.

After 72±4 hours aerobic incubation at 30±2C, colonies will be counted and viable cells in the original sample will be calculated based on the procedure *Counting Colonies on Plates and Reporting Results* (Section 6.2 K-6.2M), *Standard Methods For Evaluation of Dairy Products*, 14th Ed. American Public Health Association, Washington D.C. The plates may be stored under refrigeration for up to 48 hours prior to counting.

The average number of microorganisms recovered per cm² of skin will be determined and reported. To convert the volume of sample collected into CFU/cm² of skin, the following formula will be used:

$$R = \log_{10} \left[\frac{F \left(\frac{\sum c_i}{n} \right) 10^{-D}}{A} \right]$$

Where:

R = the average CFU count in log₁₀ scale per cm² of skin.

F = total mL of stripping fluid added to the sampling cylinder; F=6.0 mL

c/n = average of the duplicate colony counts used for each sample collected

D = Dilution factor of the plates counted

A = Inside area of the sampling cylinder (3.8 cm²)

12.4.3 Growth Promotion Control

For each batch of plating medium, Soybean-Casein Digest Agar (or equivalent) containing 0.5% Polysorbate 80 and 0.07% lecithin, fewer than 100 CFU of *Staphylococcus epidermidis*, ATCC 12228 will be inoculated in a single plate pour plate. A 20-26 hours aged culture of *S. epidermidis* will be serially diluted in dilution fluid. The CFU added will be confirmed in duplicate spread plates. The plates will be incubated for 72±4 hours at 30±2C.

13.0 DATA RECORDING

The raw data will be recorded on data collection forms for each subject. The forms will include data for screening baselines, treatment day baselines, treatment application and sampling records, and data for all evaluated sites.

All data collection forms will be provided prior to study initiation.

14.0 ASSESSMENT OF SAFETY

14.1 Skin Irritation

The safety of each test product will be evaluated by observing irritation before samples are taken at baseline and at 10 minutes \pm 30 seconds and 6 hours \pm 30 minutes after completion of prep.

14.2 Adverse Experiences

14.2.1 Definitions

Adverse Event/Experience

An Adverse Event/Experience is any unexpected or undesirable experience occurring to a subject during a study, which may or may not be related to the test article. All adverse event/experiences will be recorded and reported according to the Standard Operating Procedures of the laboratory.

All adverse events, regardless of severity or the causal/effect relationship, will be recorded. The severity of the effect will be noted as "Mild," "Moderate," or "Severe" according the following definitions:

Mild	Awareness of signs or symptom, but easily tolerated.
Moderate	Discomfort to a degree as to cause interference with normal daily life activities and /or requiring medication.
Severe	Incapacity with inability to work or do usual daily life activities and requiring medical attention/intervention.

Causal Relations of Adverse Event/Experience

When determining the causal/effect relationship to the test article, the relationship will be described as "None," "Possible," "Probable," or "Definite." The following definitions will be utilized:

None	No association to the test article. Related to other etiologies such as concomitant medications or conditions or subject's known clinical state.
Possible	Uncertain association. Other etiologies are also possible.
Probable	Clear-cut association with improvement upon withdrawal of the test article. Not reasonably explained by the subject's known clinical state but not an anticipated event.
Definite	An adverse event with a clear-cut temporal association and laboratory confirmation if possible.

Serious Adverse Event/Experience

A Serious Adverse Event/Experience is any adverse experience occurring at any dose that results in any of the following outcomes:

- Death;
- A life-threatening adverse drug experience;
- Inpatient hospitalization or prolongation of existing hospitalization;
- A persistent or significant disability/incapacity;
- Congenital anomaly/birth defect;
- An important medical event that may require medical or surgical intervention to prevent one of the previously listed outcomes.

Unexpected Adverse Event/Experience

An Unexpected Adverse Event/Experience is any adverse drug event/experience not listed in the current labeling for the test article or the current investigator's brochure. Where test article labeling or investigator's brochure is not available, anticipated experiences will be based on the known pharmacological/toxicological properties of the test article or ingredients.

14.2.2 Follow-up

If an adverse event/experience occurs, the subject under the direction of the Investigator (or designee) may be referred to the nearest acute care facility for treatment. Serious or Unexpected Drug Event/Experience will be followed to resolution. Any adverse event will be documented on an Adverse Event Report (Exhibit A).

[figure not shown]
14.2.3 Notification

The sponsor will be notified of all adverse event/experiences. Any Serious or Unexpected Adverse Drug Event/Experience that occurs during the study must be reported immediately by the investigator to the sponsor and the reviewing IRB, followed by written notification within 24 hours of the information being reported to the investigative study team.

14.2.4 Anticipated Reactions

The risks associated with this test are primarily related to application of the test article. Tape reactions are also possible. Mild to heavy erythema, swelling, itching, cracking, peeling, or in rare cases, blistering and or an allergic reaction might occur.

Occurrence of any of these events will be considered an "Adverse Event" and will be documented in the study record.

15.0 DATA AND STATISTICAL ANALYSIS

The analyses outlined below will be conducted on the data generated.

- 15.1 Raw data (CFU/mL) will be converted to \log_{10} CFU/cm². Counts of less than 1 CFU /cm² will be treated as 1 CFU/cm² such that the log transformation will be zero. Log reductions will be calculated by subtracting the post treatment log counts from the treatment day baseline counts obtained.
- 15.2 Only subjects who meet the minimum inclusion criteria for levels of bacteria on the treatment day of the study will be included in the analysis with the following exception: lab accidents resulting in contaminated samples. If there are missing data at some but not all time points, data from the available times will be included in the analysis.
- 15.3 Any subject with missing data will not be included in the data analysis. The subject with missing data will be replaced with a new subject.
- 15.4 Separate statistical analyses will be conducted for data collected from the abdomen and the groin. All hypothesis testing will be conducted at the alpha=0.05 level of significance. Data will be presented in tabular and graphical format.

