15.4.1 Microbial Data

15.4.1.1 Source Data

The source data are the CFU counted for each subject at the screening baseline and treatment day baseline evaluations and at 10 minutes and 6 hours following treatment application. The data to be used in the statistical analyses will be the R values on the skin \log_{10} of the CFU/cm² of skin on the abdomen and groin. Only baseline samples with 0 time CFU counts equal to or greater than 2.0 \log_{10} for the abdomen and with 0 time CFU counts (baseline) equal to or greater than 3.0 \log_{10} for the groin will be used to determine antimicrobial efficacy.

Data from the screening baseline and treatment day baseline evaluations in each area will be averaged to determine the combined screen and baseline count for that area. Log reductions will be calculated by subtracting the post treatment log count from the average combined screen and baseline log count for that area. Additionally, log reductions will be calculated using only the baseline data from the test day.

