15.4.1.4 Between-Treatment Analysis

- Differences between the test products will be evaluated at the 10-minute and 6-hour post treatment evaluations using analysis of covariance techniques with the average combined screening baseline and treatment day baseline \log_{10} CFU as the covariate.
- Differences between the test products will be evaluated at the 10-minute and 6-hour post treatment evaluations using analysis of covariance techniques with the treatment day baseline \log_{10} CFU as the covariate.

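### Sections 15.2 and 15.3 conflict as written on whether a subject with partly missing data is analysed, and nothing in the plan says which rule governs

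*Combined protocol and SAP*

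**What the plan says.** Two consecutive items in Section 15.0 deal with incomplete data.

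- Section 15.2 first limits the analysis to subjects who meet the treatment-day bacterial count, "with the following exception: lab accidents resulting in contaminated samples". It then says: "If there are missing data at some but not all time points, data from the available times will be included in the analysis".
- Section 15.3 says: "Any subject with missing data will not be included in the data analysis. The subject with missing data will be replaced with a new subject".

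Other sections bear on the point without settling it.

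- Section 15.4: "Separate statistical analyses will be conducted for data collected from the abdomen and the groin".
- Section 15.4.1.4: "Differences between the test products will be evaluated at the 10-minute and 6-hour post treatment evaluations using analysis of covariance techniques". Section 15.4.1.3 likewise compares baseline with each of the two times by paired t-test. No microbial model that combines the two times is named.
- Section 10.1 sets the sample size as "The requirement of 111 subjects per test article configuration (test arm) to finish this study". It foresees treating more than 278 subjects only because some will fail the test-day baseline.
- Section 12.2.2 works by area for low baselines: "Post-treatment count data will be excluded from the data analysis if they are derived from any area that fails to exhibit a level of bacteria" high enough to show the required reduction.
- Section 11.0, on withdrawal, has no rule on data or replacement.

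**The concern.** Take a subject with a valid 10-minute count and no 6-hour count. Section 15.2 keeps the 10-minute value. Section 15.3 drops the subject and enters a new one. The analyst would have to choose between them, possibly after the counts are known.

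Three consequences follow if 15.3 is applied as written.

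- **Unit of exclusion.** The subject is the unit, yet each subject has two treated sides in two body regions. One lost groin sample would remove the same subject's abdominal data, although the regions are analysed separately. It would also remove the other side's data, which may belong to a different article.
- **Dependence on a later event.** A 10-minute result would count only if the 6-hour sample also exists, so inclusion depends on something that happens after treatment.
- **Replacement.** A new subject restores the count but does not bring back the valid data that were discarded.

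**Working it through.** **The text.** The two rules applied to each kind of subject:

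| Subject | Section 15.2 | Section 15.3 |
|---|---|---|
| All data present | analysed | analysed |
| Some time points missing | available times analysed | whole subject excluded and replaced |
| Sample lost in a laboratory accident | available times analysed | whole subject excluded and replaced (no exception stated) |

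The rules differ only for partly missing subjects. Limiting 15.2 to laboratory accidents does not remove the conflict, because 15.3 covers every subject with missing data and has no matching exception.

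**The plan's own figures (Section 10.1).** Inputs: s = 0.735, difference 0.196, Z values 1.96 and 0.842.

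- n = 0.735² × (1.96 + 0.842)² / 0.196² = 110.41, rounded up to 111.
- Subjects = 5 × 111 / 2 = 277.5, rounded up to 278.
- Power at n = 111 is Φ(0.196 × √111 / 0.735 − 1.96) = 80.2%.

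The first two reproduce the protocol's figures. The conflict does not depend on any of them.

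**Subjects removed under 15.3 (illustration).** The documents give no loss rate. Let p be the average loss of post-treatment samples, assumed to be 1% (range 0.5% to 3%). Each subject gives 2 regions × 2 sides × 2 times = 8 such samples.

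| Loss pattern | Formula | p = 0.5% | p = 1% | p = 3% |
|---|---|---|---|---|
| Four 6-hour samples lost together | 2p | 1% | 2% | 6% |
| Independent losses | 1 − (1 − p)⁸ | 3.9% | 7.7% | 21.6% |

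The factor 2p arises because each affected subject loses 4 of 8 samples. Of 278 subjects, 1% loss removes about 6 in the first pattern (278 × 0.02 = 5.6) and about 21 in the second (21.5 before rounding).

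**Evaluations kept under 15.2, without replacement.**

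- Four 6-hour samples lost together: the 6-hour n per arm is 111 × (1 − 2p) = 109.9, 108.8 and 104.3 for p = 0.5%, 1% and 3%.
- Independent losses, with the treatment-day baseline needed as well as the post-treatment sample: n = 111 × (1 − p)² = 109.9, 108.8 and 104.4.
- Power by the same formula is 79.8%, 79.4% and 77.8% in both patterns.

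**The case against.** The best defence is that the two items were meant for different cases. In 15.2 the available-times sentence directly follows the laboratory-accident exception and can be read as explaining it. Section 15.3 would then cover subjects who do not finish, which fits the wording of the sample-size requirement in Section 10.1. This is a sensible guess at intent, and for that reason it would overstate the point to call the two rules irreconcilable. But neither limit is written, and a non-finisher with a 10-minute sample is also the partial-data case that 15.2 keeps. Section 10.1 supports replacement; it does not say that valid data from the replaced subject are thrown away.

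A second objection also has force: analysing complete subjects only, with replacement, would be a coherent rule and would resolve the conflict too. What the plan requires is a single rule. The choice of available data is a preference, though a reasoned one, because it keeps valid data and does not make inclusion depend on a later sample.

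A third objection is that the size rests entirely on assumptions. That stands. Post-treatment sampling ends about six hours after application, so losses may be few, and the documents do not favour either loss pattern.

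**Conclusion.** The conflict is in the text and is certain: for partly missing subjects the analysis set is undetermined, and the plan should be corrected. High confidence applies to that conflict. It does not extend to the magnitude or to the choice of rule. Subjects with complete data are treated alike under both rules.

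A reader might infer two stronger things.

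- **That the results would be biased.** Selection is possible because 15.3 ties inclusion to a later sample, but the documents give no reason or rate for missing samples, so bias is not shown.
- **That large losses should be expected, larger still if baseline samples are counted.** The percentages are illustrations at assumed rates. Adding lost treatment-day baselines would not measure the difference between the rules, because an area without that baseline is largely unusable under 15.2 as well; only the subject's other areas would differ.

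The baseline cut-offs in Sections 12.2.2 and 15.4.1.1 also differ. That concerns low counts, not missing data, and is a separate matter.

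**What to change.** State in Section 15.0 one missing-data rule, its unit, and the replacement policy. The preferred wording would:

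- apply the available-data rule of 15.2 by treated area and time point, and delete the whole-subject exclusion in 15.3;
- say whether subjects are replaced to keep 111 evaluations per arm and, if so, keep the replaced subject's valid data in the analysis;
- say that an area with no treatment-day baseline cannot be shown to meet the Section 12.2.2 criterion and is left out of the efficacy analysis, while the subject's other areas stay in;
- say how the laboratory-accident exception in 15.2 operates under this rule.

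This is a change of wording; the tests and the sample size stay as they are. It has three costs. The n per time point becomes slightly unequal. An area missing one irritation time has no two-time average for Section 15.4.2.3, whose definition should be left alone. If subjects are not replaced, power falls by 0.8 percentage points at the assumed 1% loss (80.2% − 79.4%), and by 0.4 to 2.4 points over the range.
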